They contribute and maintain the functionality and integrity of the eye's sensitive structures (retina, iris, lens), preventing or reducing the damages caused by free radicals. In specialized literature is largely described their high antioxidant

	activity and the advantages of a consumption or supplement. Lutein and zeaxanthin pass through the placental barrier, they are also present in the colostrums and breast milk and it is believed that they take part to the embryogenesis of the retina and to the development of visual functions during the first weeks of life. As a result, the lutein and zeaxanthin are essential to the health of the eye, both on adults and children suring their first hours of life. Thus, the absorption of these substances proves to be necessary in situations of necessity growth or in case of deficient intake, both during the aging period of the ocular structures responsible for the visual function (macula), and during their conservation period. The lutein and zeaxanthin do not present contraindications and can be taken at any age. Use: LUTEIN ofta 0,5 gocce is indicated in situations of necessity growth or in case of deficient food intake of its components on different age groups. LUTEIN ofta 0,5 gocce can be useful especially in preventing macular or retina damages.	
Study Objectives	Main objective	
, and a second s	To evaluate if the administration of pharmacology doses of Lutein/Zeaxanthin micronutrients in water (LUTEIN ofta 0,5 gocce – Neoox) is able to reduce the level of radicalemy and at the same time to elevate the antioxidant power of premature newborns (gestational age: \leq of 32 weeks and / or weight at birth: \leq 1500 grams).	
Study scketch	pilot study, non-commercial, with food supplement, treated vs. control with a	
	ratio 1: 1 double-blind. The identical vials, corresponding to placebo and active product, have an alphanumeric code without meaning for the operator, but that identifies the traty from control, in an anonymous document kept by the Statistical. The document will be placed in a sealed and anonymous envelopeand it will be kept open by the statistician at the time of data analysis.	
People	Inclusion criteria	
participating at	• Newborns with a weight ≤ 1.500 grams and/or gestational age ≤ 32 weeks;	
the study and their number	Male and female newborns; Newborns where reports went to sign the information forms informed.	

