number	• Newborns whose parents want to sign the information form – informed consent.	
	Consent	
	Exclusion criteria	
	• Informed consent is not signed	
	 Infants of birth weight ≥ 1.500 gramms and/or gestational age > 32 weeks infants hospitalized after 36 hours of life 	
	Infants with ophthalmologic disease at randomization	
	• infants with severe malformations	
	Number of nationts about to be varietaved	
	Number of patients about to be registered It is expected to register a total number of 50 newborns divided in two groups:	
	• Experimental group A: 25 newborns treated;	
	Control group B: 25 newborns treated.	
Randomization	Subsequently enrollment patients will be randomly divided into Group A and Group B throught a web system that allows the randomization into three different recruitment centers	

	T
Number of centres	Multicenter pilot study. At the study will participate three Italian experimental centres: Naples, Siena and
	Padova.
	The centre from Naples will be the national coordinator and the center from Siena
	will handle in a centralized way the laboratory results. The center from Padova
	will help to recruit an adequate number of cases.
Sample size	BAP and TH are two bio-markers with different hypothetical changes clearly different. For this reason we will use the study method proceeds by the following online site http://clincalc.com/stats/samplesize.aspx (Rosner B. Fundamentals of Biostatistics. 7th ed. Boston, MA: Brooks/Cole; 2011). The inserted reference values are for BAP 2361 (\pm 466) μ mol/L and for TH 156.75 (\pm 64.0) Ucarr (Perrone S., Longini M. et. Al). The difference for BAP that we hypothesize to find is an increase of at least 500 μ mol / L which is approximately 20% of the control data. By setting α = 0.05% and β =0.1% with a power of 90% the number of samples required is 25 + 25 = 50. For the TH assume a decrease of 50 Ucarr which is approximately 30% of the
	data of the control. By setting $\alpha = 0.05\%$ and $\beta = 0.2\%$ with a power of '80% also in this case the required number of samples is $25 + 25 = 50$.
	However $25 + 25$ is the minimum number. Taking into account any ongoing study waivers (parents may request to discontinue treatment at any time) which go beyond statistical calculations. So in case of necessity we will recruit a number of infants to reach the minimum number according to the design of the protocol (25 $+$ 25).
Treatment and	Products administered:

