laboratory investigations foreseen. The second semester will be used to study and analyse the results achieved.

Procedures

Methodology:

When born, premature newborns that are comply with the inclusion parameters will be introduced and separated in two random groups (A and B).

All newborns, during the observation period, will be submitted to the blood collection (1 ml) from the umbilical cord and peripheral (at the same time with the routine collections) on which there will be performed blood gas analysis and oxidative stress markers (TH and BAP). All registered newborns will also be submitted to the verification of their history concerning the examination and collection, in view of evaluation the presence or absence of ROP, NEC, IVH, BPD and infections.

Collection Time

- T0, basic at birth, before begining the treatment: blood collection from the umbilical vein.
- T1, first check, to 15 days after initiation of treatment: peripheral blood collection in view of verifying it before the Lutein/zeaxanthin administration.
- T2, second check, at 30th day since the begining of treatment: peripheral blood collection in view of verifying it before the Lutein/zeaxanthin administration.

The parents will be informed concerning the experimental procedure and the checks schedules.

It will be required the written consent of the parents.

The protocol shall be submitted to approval to the local ethics commission.

Evaluation Parameters:

Efficiency:

a) Evaluation of oxidative stress biomarkers in the peripheral blood of the premature newborn before and after the treatment.

Tolerability:

There will be transcribed on the data sheet possible adverse events which may be observed by the doctor.

Evaluation Scale

- a) Evaluation of the oxidative stress: by deremining the oxidative stress biomarkers and registering them in the data sheet.
- b) They must be indicated:

Demographic Characteristics

- Sex
- Gestational Age
- Weight (with percentile)
- Mode of delivery
- Preeclampsia
- Premature rupture of membranes
- Using steroids before birth
- Using antibiotics before birth
- Use of drugs or harmful substance before birth

Clinical features

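### Read as written, the weight and gestational-age exclusion removes every infant who meets only one prematurity criterion, although the main objective and inclusion line admit them

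*Combined protocol and SAP*

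**What the plan says.** Three places in the combined protocol and SAP define the population by weight and gestational age.

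- **Study Objectives, Main objective.** The target is premature newborns, with the two limits (32 weeks, 1500 g) joined as "of 32 weeks and / or weight at birth". Either is enough.
- **People participating at the study, Inclusion criteria.** The same rule: "Newborns with a weight ≤ 1.500 grams and/or gestational age ≤ 32 weeks".
- **People participating at the study, Exclusion criteria.** The excluded group is "Infants of birth weight ≥ 1.500 gramms and/or gestational age > 32 weeks".

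Two further places bear on how the rule is applied. Under Procedures (Methodology), "premature newborns that are comply with the inclusion parameters will be introduced and separated in two random groups"; exclusions are not mentioned there. Under Randomization, allocation uses "a web system that allows the randomization into three different recruitment centers".

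**The concern.** The opposite of *A or B* is *neither A nor B*. If an infant enters by meeting either criterion, the matching exclusion must require that both fail. The exclusion line reverses each inequality but keeps *and/or*, so on the ordinary reading failing one criterion is enough to be excluded. Infants who qualify on one criterion alone then satisfy both the inclusion and the exclusion.

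Two things are at stake. First, if the exclusion is followed, the trial never studies a group that its main objective explicitly names, and its result describes a different population. Second, three centres recruit. Nothing in the documents tells them which line prevails, so they could treat the same kind of infant differently, and it could not be said whether a given enrolment is a protocol deviation. There is little time for a query: groups are formed at birth and the first dose is due within 36 hours of life. With 50 infants planned, each one is 1/50 = 2% of the sample.

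**Working it through.** The plan gives no figure to reproduce here; this is a check of logic.

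**Inputs**

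- Included (Main objective and Inclusion criteria): BW ≤ 1500 g OR GA ≤ 32 weeks.
- Excluded (Exclusion criteria): BW ≥ 1500 g *and/or* GA > 32 weeks.
- Eligible = included and not excluded.

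The exclusion was applied in four forms: *and/or* taken as OR or as AND, and the weight sign taken as ≥ (as printed) or as > (in case ≥ is an error of text extraction). Weight is split at exactly 1500 g because that value meets both printed limits.

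| GA (weeks) | BW (g) | Included? | OR, ≥ | OR, > | AND, ≥ | AND, > |
|---|---|---|---|---|---|---|
| ≤ 32 | < 1500 | yes | eligible | eligible | eligible | eligible |
| ≤ 32 | = 1500 | yes | removed | eligible | eligible | eligible |
| ≤ 32 | > 1500 | yes | removed | removed | eligible | eligible |
| > 32 | < 1500 | yes | removed | removed | eligible | eligible |
| > 32 | = 1500 | yes | removed | removed | removed | eligible |
| > 32 | > 1500 | no | – | – | – | – |
| **Left of 5** | | | **1** | **2** | **4** | **5** |

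**Results**

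1. The objective covers 5 of the 6 cells.
2. With OR and the printed sign, 5 − 4 = 1 cell is left: BW < 1500 g and GA ≤ 32 weeks.
3. With OR and >, 5 − 3 = 2 cells are left: BW ≤ 1500 g and GA ≤ 32 weeks.
4. The three single-criterion cells (rows 3, 4 and 5) are removed under OR with either sign. An infant who meets only the weight criterion has GA > 32 weeks, and one who meets only the gestation criterion has BW > 1500 g, so each triggers the exclusion.
5. With AND, the only loss is an infant of exactly 1500 g and above 32 weeks, and only with the printed ≥.

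**Worked cases.** At 31 weeks and 1700 g, GA ≤ 32 includes the infant and BW > 1500 excludes it under OR. At 33 weeks and 1300 g, BW ≤ 1500 includes the infant and GA > 32 excludes it under OR. Under AND neither infant is excluded, whichever sign is used.

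Cells are categories, not shares of infants. The split at exactly 1500 g raises the count of cells removed. On a plain two-by-two table (≤ or > 1500 g by ≤ or > 32 weeks, with > for weight), OR removes 2 of the 3 included cells. The finding is the same.

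**The case against.** The best reply is that this is a slip of drafting. *And/or* carries both senses. If the exclusion is read as *and*, the conflict disappears except at exactly 1500 g. The objective, the inclusion line and the enrolment step under Procedures all point to the broad population, and the exclusion looks like a mirror image of the inclusion in which the connector was not changed. On that view the enrolled population need not be narrower, and inconsistency between centres is only a possibility. The documents do not show it, nor do they say whether the web system checks eligibility.

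Part of this stands. The broad population may well be what was intended, the narrowing depends on reading the exclusion as written and letting it prevail, and the counts of cells are not an effect size.

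It does not remove the problem. The enrolment step refers only to inclusion parameters and does not switch off the exclusions, which normally still apply. The opposite intent, requiring both criteria, fits the exclusion as printed. Staff at three centres should not have to infer which was meant.

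**Conclusion.** The concern holds. On the ordinary inclusive reading of *and/or*, the exclusion contradicts the main objective and the inclusion line for every infant who meets only one criterion. It leaves 1 of the 5 stated categories (2 if the weight sign should be >). This rests on two assumptions: that *and/or* means OR, and that an exclusion overrides an inclusion. If *and* was meant, 4 or 5 of the 5 categories survive.

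The overlap at exactly 1500 g is secondary, and the main mismatch does not depend on it. The number of infants affected cannot be given. Eligibility is settled before the 1:1 double-blind allocation, so the point concerns whom the result describes and consistency across centres. It does not concern bias between arms, variance, power or type I error. It should be fixed, and confidence is high.

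**What to change.** Before enrolment, reconcile the objective, inclusion and exclusion lines into one rule applied at all three centres. The choice of population is the sponsor's.

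- **If either criterion suffices, as the objective now states:** change the exclusion to birth weight > 1500 g AND gestational age > 32 weeks, or delete that clause alone. The restated exclusion removes 0 of the 5 stated categories.
- **If both criteria are required:** change *and/or* to *and* in the inclusion line and the main objective, and make the exclusion birth weight > 1500 g OR gestational age > 32 weeks. It then removes 0 of the 2 stated categories (< 1500 g and = 1500 g, each at ≤ 32 weeks). This narrows the recruitment pool relative to the present objective.

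Both versions also settle the 1500 g boundary. In either case keep the separate exclusion of "infants hospitalized after 36 hours of life", which runs on from this clause in the extracted text.

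The cost is one clause, or three lines for the second option, plus a notice to the three centres. The protocol goes to the local ethics commission, so if approval has already been given the change may need to be resubmitted. The calculated sample size, the randomisation and the analysis do not change.

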	 Apgar score Use of surfactant Umbilical catheter CVC location and duration Intubation Mechanical ventilation (procedures and time) Supplementation of O2 Incidence of infections Use and type of antibiotics Use and type of antifungal Use and type of post-natal steroids Use and type inotropic Use of NPT Duration of treatment in NICU Nutritional Characteristics: Oral feeding start time Exclusive oral feeding start time Fluid volume Intake calories (protein, carbohydrates and fats) Use of maternal and /or uman milk Other therapies associated and/or permitted During the trial period it is not permitted any product administration or antioxidant activities (anti-radicals) or products which contain even a sole
Basic examination	component having this result, excepting the protocol. At birth, as it is foreseen by newborn protocols, the babies will be submitted to
	several medical examinations.
Control examination	From the Birthing Unit, the newborns will be transered to intensive care rooms where they will be submitted to multiple control examinations.
Follow-up examinations	As it is foreseen in neonatal protocols.
Statistical Analysis	The Student t test for independent data is the type of analysis that will be used to assess statistically significant differences between the parameters recorded in the two groups (treated and control). The Student t test is the method of choice for analysis as it allows to evaluate the values of a continuous random variable measured in not very many samples (25 subjects per group). It will be using the statistical package SPSS system.

REFERENCES

Lutein: description, pharmacokinetics activity and characteristics, mechanism of action, safety and tolerability

- 1. Shao, A. and Hathcock, JN. Risk assessment for the carotenoids lutein and lycopene. Regul Toxicol Pharmacol. 2006 Aug;45(3):289-98.
- 3. Khachik F, de Moura FF, Chew EY, Douglass LW, Ferris FL 3rd, Kim J, Thompson DJ. The effect of lutein and zeaxanthin supplementation on metabolites of these carotenoids in the serum of persons aged 60 or older. Invest Ophthalmol Vis Sci. 2006 Dec;47(12):5234-42.

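### Sample size: the error rates are misprinted as percentages, and the inputs do not give 25 per group for either marker (BAP 20, TH 27 by two-sided 5% t test)

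*Combined protocol and SAP*

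**What the plan says.** The Sample size section makes two calculations with an online calculator. For BAP it takes a reference value of 2361 (SD 466) µmol/L and a hypothesised increase of at least 500. It then states "α = 0.05% and β =0.1% with a power of 90% the number of samples required is 25 + 25 = 50". For TH it takes 156.75 (SD 64.0) Ucarr and a decrease of 50, prints alpha as 0.05% and beta as 0.2%, and continues "with a power of '80% also in this case the required number of samples is" 25 + 25 = 50. It calls 25 + 25 the minimum and allows extra recruitment only to get back to that number.

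The Statistical Analysis section says "The Student t test for independent data is the type of analysis that will be used" to compare treated and control infants. It gives neither a significance level nor the sidedness of the test.

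**The concern.** There are two problems. First, the printed error rates conflict with the stated power: power is 1 − beta, so a beta of 0.1% or 0.2% cannot sit beside 90% or 80%. The printed alpha of 0.05% does not conflict with its own sentence, but it is a hundred times stricter than the usual 5%, and no other section supplies a level.

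Second, two markers with different standardised differences (500/466 = 1.073 and 50/64 = 0.781) and different power targets are reported to need exactly the same number. At least one of the two results is then unlikely to follow from its inputs.

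What is at stake is whether the threshold for the t tests is fixed correctly before the treatment code is opened, and whether the stated power is the power the design has.

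**Working it through.** **Inputs.** Sample size section: BAP difference 500, SD 466, power 90%; TH difference 50, SD 64, power 80%. Study sketch: allocation 1:1. Statistical Analysis: independent-samples t test. Sidedness is not given, so both are tried.

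**Formula.** Normal approximation, n per group = 2(z_α + z_β)²(SD/δ)², rounded up. The t-test number is the smallest n whose noncentral-t power reaches the target.

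**Trying to reproduce 25, two-sided 5%.**
- BAP: 2(1.960 + 1.282)²(466/500)² = 18.25, so 19. By t test, 19 gives 89.6% power and 20 gives 91.1%, so 20.
- TH: 2(1.960 + 0.842)²(64/50)² = 25.72, so 26. By t test, 26 gives 78.9% and 27 gives 80.4%, so 27.

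**Other readings, n per group at the stated power.**

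| Alpha | BAP, normal / t | TH, normal / t |
|---|---|---|
| 5% two-sided | 19 / 20 | 26 / 27 |
| 5% one-sided | 15 / 16 | 21 / 21 |
| 0.05% two-sided, as printed | 40 / 43 | 62 / 65 |

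If the printed betas are also taken literally, the normal formula gives 76 (BAP) and 133 (TH). The plan's rounded effects, at two-sided 5%, do not help either: 20% of 2361 = 472 gives 21 or 22 for BAP, and 30% of 156.75 = 47 gives 30 or 31 for TH. None of these readings gives 25 for either marker.

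**Power at 25 per group, two-sided 5%.** The noncentrality is (δ/SD)√(25/2).
- BAP: 1.073 × 3.536 = 3.79. Normal power is Φ(3.79 − 1.96) = 96.7%; t-test power is 96.1%.
- TH: 0.781 × 3.536 = 2.76. Normal power is Φ(2.76 − 1.96) = 78.9%; t-test power is 77.2%.

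At one-sided 5% the t-test power is 98% for BAP and 86% for TH.

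**Differences detectable at 25 per group, two-sided 5% t test.** TH: 51.8 Ucarr at 80% power, against the 50 assumed. BAP: 436 µmol/L at 90% power, against the 500 assumed.

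**If alpha really were 0.05%.** At 25 per group the two-sided t-test power would be 53% for BAP and 19% for TH. This supports reading the percent sign as a slip.

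**The case against.** The strongest reply is that little harm follows. The intended values are easy to guess, the study is a pilot, and 25 per group is more than BAP needs. For TH the plan relies on an online calculator whose formula it does not show. The normal formula gives 25.72, so the printed 25 may simply be that value cut instead of rounded up, which is one infant per group and about one point of power. The figure of 27 comes from an exact t-test calculation that the plan never claims to have made. The hypotheses are also worded directionally (an increase in BAP, a decrease in TH), and with a one-sided 5% test 25 is enough for both markers.

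Much of this stands as a limit on the size of the problem. The TH gap is small and depends on two-sided testing, and the BAP error is on the safe side. It does not rescue the text. Truncation could explain TH but not BAP, where 25 does not follow under either sidedness. A directional hypothesis does not by itself specify a one-sided test. The betas can be inferred from the stated power, but nothing printed confirms the alpha, and sidedness cannot be inferred at all. Replacing infants who leave only restores 25 + 25, so it does not close the TH gap.

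**Conclusion.** The concern holds. The printed betas contradict the stated power, and the only significance level in the document is, on any sensible reading, a misprint. The statement that both markers require 25 per group does not follow from the inputs. Assuming a two-sided 5% t test, BAP needs 20 and TH needs 27 (19 and 26 by the normal formula). The planned 25 per group gives about 96% power for BAP instead of 90%, and about 77% for TH instead of 80%.

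The BAP discrepancy is a conservative documentation error. The TH shortfall is 1 or 2 infants per group and rests on two-sided testing, which the plan does not state; one-sided, 21 per group would do. The text should be corrected, but the trial's size is not called into serious question.

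**What to change.** Keep 25 + 25 and correct the text.

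- In Sample size, print alpha = 0.05 (5%), and beta = 0.10 for BAP and 0.20 for TH. State the sidedness; two-sided is recommended.
- Repeat the level and sidedness in Statistical Analysis, before the code is opened.
- Give the required number for each marker and name the method: BAP 20 and TH 27 per group by two-sided t test, or 19 and 26 by the normal formula. Say that TH drives the total.
- State what 25 per group delivers by t test: about 96% power for BAP and about 77% for TH, or 80% power for a TH difference of about 52 Ucarr.
- Reword the sentences that call 25 + 25 the minimum, so that they describe a chosen size and do not contradict a TH requirement of 27.
- Optionally, say which population the planning SDs come from. The background describes the earlier work on these markers as being in term infants, and the Sample size citation appears to be to that work.

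The cost is wording only, with no extra infants. The stated TH power falls by about 3 points and the stated BAP power rises by about 6.

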Way of intake Duration of the period of administration	Products administered: LUTEIN ofta 0,5 gocce, containing a solution of 5% Lutein and 2,25% Zeaxanthin with excipients (Corn starch, glucose, potassium sorbate, xanthan gum, citric acid) (group A) Placebo solution with unique excipients (Demineralised water, potassium sorbate, xanthan gum, citric acid) (group B) Experimental Group: Group A (25 newborns) will be treated with LUTEIN ofta 0,5 gocce, (1 ml per Kg equal to 0,5 mg of lutein and 0,05 of zeaxantin), divided in two additional administrations during the day from the standard hospital treatment foreseen. The first dose will be given within 36 hours of life, the least to 30th day of life. Control Group: Group B (25 newborns) treated with Placebo solution (additionaly to the standard hospital treatment foreseen. The first dose will be given within 36 hours of life, the least to 30th day of life. The product will be administered by adding it in the milk (human or formulae), or in a small quantity of glucose, either orally or by gavage. The administration of the product (LUTEIN ofta 0,5 gocce) starts within the first 36 hours of life and continues with daily administration for 30 days.
Way of intake Duration of the period of administration	Products administered: LUTEIN ofta 0,5 gocce, containing a solution of 5% Lutein and 2,25% Zeaxanthin with excipients (Corn starch, glucose, potassium sorbate, xanthan gum, citric acid) (group A) Placebo solution with unique excipients (Demineralised water, potassium sorbate, xanthan gum, citric acid) (group B) Experimental Group: Group A (25 newborns) will be treated with LUTEIN ofta 0,5 gocce, (1 ml per Kg equal to 0,5 mg of lutein and 0,05 of zeaxantin), divided in two additional administrations during the day from the standard hospital treatment foreseen. The first dose will be given within 36 hours of life, the least to 30th day of life. Control Group: Group B (25 newborns) treated with Placebo solution (additionaly to the standard hospital treatment foreseen. The first dose will be given within 36 hours of life, the least to 30th day of life. The product will be administered by adding it in the milk (human or formulae), or in a small quantity of glucose, either orally or by gavage. The administration of the product (LUTEIN ofta 0,5 gocce) starts within the first 36 hours of life and continues with daily administration for 30 days. Duration of the observation period of the patient registered

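### The top-up to 25 + 25 most naturally leads to a comparison of infants who did not stop, and the readable text names no analysis set

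*Combined protocol and SAP*

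**What the plan says.** The Sample size row says that 25 + 25 "is the minimum number. Taking into account any ongoing study waivers (parents may request to discontinue treatment at any time", places such cases outside the statistical calculation, and answers them with further recruitment: "So in case of necessity we will recruit a number of infants to reach the minimum number according to the design of the protocol".

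The Statistical Analysis row plans a Student t test between treated and control, chosen because the variable is "measured in not very many samples (25 subjects per group". It names the test and the software. Neither it nor any other readable part of the protocol names an analysis set or a rule for missing values.

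The Procedures section states: "All newborns, during the observation period, will be submitted to the blood collection (1 ml) from the umbilical cord and peripheral". Sampling is at T0, T1 (15 days) and T2 (30 days). The row headed "Duration of the observation period of the patient registered" breaks off in the available text, so anything it said about follow-up after stopping cannot be seen.

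Allocation is 1:1, through "a web system that allows the randomization into three different recruitment centers". On blinding, the study sketch says: "The identical vials, corresponding to placebo and active product, have an alphanumeric code without meaning for the operator".

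**The concern.** Recruiting back to a fixed number because some infants stop makes most sense if those infants no longer count towards that number. The t test would then compare infants who stayed on the product, a group selected after randomisation. If infants with worse oxidative stress are more likely to stop, and more of them stop in one arm, that arm looks better on TH and BAP for a reason unrelated to the product.

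A link between stopping and the outcome is plausible, though not shown: the protocol's background section ties oxidative stress to ROP, IVH, BPD, NEC and infections in preterm infants, and treatment lasts 30 days. Even if the sponsor means to analyse everyone, the plan does not say so. The study sketch has the statistician use the sealed allocation document at the time of data analysis, so the choice of infants could be made with allocation known.

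**Working it through.** **Inputs.** From the Sample size row: TH SD 64.0 Ucarr, target decrease 50; BAP SD 466 µmol/L, target increase 500; 25 per arm. Alpha and beta are printed with percent signs. I read them as alpha 0.05 with 90% power (BAP) and 80% power (TH), and assume two-sided tests because sidedness is not stated. The protocol gives no stopping rate and no difference between infants who stop and those who continue, so both are assumptions below.

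**1. The plan's own figure.** n per arm = 2 (z₀.₉₇₅ + z₁₋β)² (SD/δ)².
- TH: 2 × (1.960 + 0.842)² × (64/50)² = 25.7, so 26 against the stated 25.
- BAP: 2 × (1.960 + 1.282)² × (466/500)² = 18.3, so 19.

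TH drives the size and is reproduced to within one infant per arm. Neither calculation allows for stopping; the top-up takes the place of such an allowance.

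**2. The passages side by side.** If infants who stop the product were still sampled and counted, stopping would leave no shortfall to refill. The Sample size row foresees a shortfall, and the Statistical Analysis row repeats 25 per group. Together these point to a completers comparison. Two things point the other way: 25 + 25 is called a minimum, and Procedures has all newborns sampled. Exclusion is therefore an inference.

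**3. Bias if infants who stop are left out.** Let both arms have true mean µ. A fraction p stops, and infants who stop have a mean s above the completers of their arm, whose mean is c. Then µ = (1 − p)c + p(c + s), so c = µ − ps, and the completers difference is −(p_A − p_B)s. The arm with more stopping looks better. The standard error is SD × √(2/25): 64 × 0.2828 = 18.1 for TH and 466 × 0.2828 = 131.8 for BAP. Type I error comes from the noncentral t distribution with 48 df and noncentrality bias/SE. With s = 1 SD (TH higher, BAP lower):

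| Stopping, A v B | TH bias (Ucarr) | Share of 50 | BAP bias (µmol/L) | Type I error |
|---|---|---|---|---|
| 20% v 20% | 0 | 0% | 0 | 5.0% |
| 20% v 15% | 0.05 × 64 = 3.2 | 6% | 23.3 | 5.3% |
| 20% v 10% | 0.10 × 64 = 6.4 | 13% | 46.6 | 6.4% |
| 20% v 0% | 0.20 × 64 = 12.8 | 26% | 93.2 | 10.7% |

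With s = 0.5 SD, 20% v 10% gives 0.10 × 32 = 3.2 Ucarr and 5.3%. A simulation of the same model (60,000 runs, 25 completers per arm) gave 5.0%, 5.3%, 6.4% and 10.7% for the four rows. If every randomised infant is sampled and analysed as assigned, the same model gives 4.9% to 5.1% throughout; that is a best case.

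**4. Power if all are analysed.** Suppose 10% of the treated arm stop and get no benefit.
- TH effect: 0.9 × 50 = 45 Ucarr. Noncentrality falls from 50/18.1 = 2.76 to 45/18.1 = 2.49, and power from 77.2% to 68.3%.
- BAP effect: 0.9 × 500 = 450 µmol/L. Power falls from 96.1% to 91.7%.

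**The case against.** The protocol never says that infants who stop are excluded. A reader might infer that it does, but calling 25 + 25 a minimum leaves room to analyse more than 50, and the figure of 25 per group is offered as a reason for choosing a t test, not as a definition of who is analysed. This stands, so exclusion can only be called the most natural reading.

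The trigger is also unclear. The sentence speaks of study waivers and only in parentheses says that "parents may request to discontinue treatment at any time". If a waiver means leaving the study, there is no T1 or T2 sample to exclude, the top-up is ordinary cover for missing outcomes, and analysing every infant with a sample changes little. This also stands, and it limits what the fix can achieve.

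A reader might further infer that infants who stop are not sampled. The documents do not support that: Procedures covers all newborns, and the observation-period text is broken. Nor does recruiting more infants in itself break the randomisation.

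Finally, the bias needs exclusion, selective stopping and unequal stopping together, and identical coded vials work against the last. Leaving aside the extreme 20% v 0% row, the largest TH bias shown is 6.4 Ucarr, about a third of the standard error (6.4/18.1 = 0.35). That is modest for a pilot study. It lowers the urgency but does not tell the analyst which infants to include.

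**Conclusion.** The point holds as a defect in the analysis rule. The text recruits back to 25 + 25 in response to stopping, tests 25 per group, and names no analysis set in its readable parts. Followed as written, it most naturally gives a completers comparison instead of a comparison of the groups as randomised.

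The size rests on assumed stopping rates and an assumed 1 SD difference. In moderate scenarios type I error is 5.3% to 6.4%. It is 5.0% when stopping is equal and the product has no effect, and 10.7% only in a case that blinding makes unlikely. A reader might infer a large false-positive risk from this; the documents give no figures that would support it. The reason to act is that the analysis population is undefined and cheap to define before the code is opened.

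**What to change.** Keep the top-up sentence, reworded, and add an analysis rule.

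1. **Recruitment.** Extra infants are additions, randomised 1:1 through the same web system, until at least 25 infants per arm have a T2 sample, whether or not the product was stopped. The pooled count is followed without opening the code. Because a pooled 50 does not guarantee 25 in each arm, the trigger can be set slightly above 50; a 27 v 23 split changes the TH standard error only from 18.1 to 64 × √(1/27 + 1/23) = 18.2.
2. **Primary t test.** Include every randomised infant with a sample at the visit, in the assigned arm, whether or not the product was stopped.
3. **Sampling.** State that the T1 and T2 sampling of all newborns in Procedures continues after the product is stopped, unless the parents withdraw consent to sampling.
4. **Reporting.** Give deaths and other missing samples by arm, separately. Present the completers analysis as sensitivity only. Any penalty for missing values in a further sensitivity analysis is an assumption for the sponsor to fix before unblinding.

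**Cost.** Protocol and consent wording for sampling after stopping, and the samples themselves (1 ml, at the same time as routine collections). The main statistical cost is the dilution shown above. If the sponsor wants to recover TH power under 10% stopping, 28 analysed per arm gives 73% and 33 gives 80%. Infants withdrawn from sampling remain missing, so the rule limits the bias but does not remove it.
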